4.4.1.2. Intensity of Adverse Events

Intensity (or severity) of AEs will be graded as “Mild”, “Moderate” or “Severe”. For AEs with missing severity, the most severe assessment will be imputed for analyses, following worst case principle.

4.4.1.3. Relationship to Study Drug

Causal relationship of AEs with study drug will be classified by the Investigator and will be reported as follows:

- Not related
- Unlikely related
- Possibly related
- Probably related

Related AEs are AEs with the relationship described by the investigators as “probably related” or “possibly related”. “Not related” or “Unlikely related” causality assessments are considered as negative causality.

Any missing relationship of an AE to study drug will be considered as related to study drug for the analyses, following worst case principle.

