9.3.2.1. Adverse Events

AEs will be coded using Medical Dictionary for Regulatory Activities (MedDRA) by preferred term within system organ class. The number of AEs and the number of subjects reporting AEs will be listed and summarized descriptively by body system, preferred term, severity, and causality. By-subject listings of AEs will be provided.

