10.3.1. Definitions

An AE is any unfavorable or unintended change in body structure (signs), body function (symptoms), laboratory result (eg, chemistry, ECG, X-ray, etc), or worsening of a pre-existing condition associated temporally with the use of the study medication whether or not considered related to the study medication. AEs will be captured once a subject has signed the informed consent. AEs include:

- Changes in the general condition of the subject.
- Subjective symptoms offered by or elicited from the subject.
- Objective signs observed by the investigator or other study personnel.
- All concurrent diseases that occur after the start of the study, including any change in severity or frequency of pre-existing disease.
- All clinically relevant laboratory abnormalities or physical findings that occur during the study.

A treatment-emergent AE (TEAE) is any condition that was not present prior to treatment with study medication but appeared following treatment, was present at treatment initiation but worsened during treatment, or was present at treatment initiation but resolved and then reappeared while the individual was on treatment (regardless of the intensity of the AE when the treatment was initiated).

A SAE is defined as an AE that:

- Results in death.
- Is immediately life-threatening (there is an immediate risk of death from the AE as it occurred; this does not include an AE that had it occurred in a more serious form may have caused death).
- Results in or prolongs an inpatient hospitalization (Note: a hospitalization for elective or preplanned surgery, procedure, or drug therapy does not constitute an SAE).
- Results in permanent or substantial disability (permanent or substantial disruption of one's ability to conduct normal life functions).
- Is a congenital anomaly/birth defect (in offspring of a subject using the study medication regardless of time to diagnosis).
- Is considered an important medical event.

Important medical events are defined as events that, based upon appropriate medical judgment, may jeopardize the subject and may require medical or surgical intervention to prevent one of the other serious outcomes. Examples of important medical events include allergic bronchospasm requiring intensive treatment in an emergency room or at home, blood dyscrasias or convulsions that do not result in inpatient hospitalization, or the development of drug dependency or drug abuse.

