10.3.2. Relationship to Study Drug

The degree of “relatedness” of the AE to the study medication must be described using the following scale:

- **Not related** indicates that the AE is definitely not related to the study medication.
- **Unlikely related** indicates that there are other, more likely causes and study medication is not suspected as a cause.

- **Possibly related** indicates that a direct cause and effect relationship between study medication and the AE has not been demonstrated, but there is evidence to suggest there is a reasonable possibility that the event was caused by the study medication.
- **Probably related** indicates that there is evidence suggesting a direct cause and effect relationship between the AE and the study medication.

It is the sponsor's policy to consider "Probably related" and "Possibly related" causality assessments as positive causality. "Not related" and "Unlikely related" causality assessments are considered as negative causality.

Assessments will be recorded on the eCRF and must indicate clearly the relationship being assessed. For example, an AE that appears during a placebo run-in phase would be assessed with respect to the placebo treatment received and/or study procedures conducted during this phase. If the AE continued into an active treatment phase, the relationship would be assessed for the active treatment phase only if the AE worsened.

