3. STUDY DESIGN AND MEASURES

3.1. Study Design

This is a Phase 2b, open-label, exploratory study of the mechanism of action of bruising and safety of CCH subcutaneously administered in subjects undergoing elective abdominoplasty surgery.

Approximately 8 subjects (1 or 2 subjects per group) were originally expected to enroll and complete the study (on Day 28). An additional 2 subjects will be enrolled to replace (for overall

objective and endpoint analysis purposes) subjects whose abdominoplasty surgeries were delayed due to COVID-19 restrictions. The 2 subjects whose surgeries were delayed due to COVID-19 can still undergo planned abdominoplasty surgery at a time convenient to both the investigator and the subject, and complete the study, but will be excluded from the non-safety analysis population. Subjects who are considered screen failures due to logistic/timing purposes surrounding the subject's availability for surgery (excluding any other inclusion/exclusion criteria reasons) and/or COVID-19 restrictions, may be rescreened. Subjects who undergo elective abdominoplasty surgery and are willing to receive injections of CCH and have their tissue donated for evaluation (otherwise discarded post-surgery) will be eligible, provided all inclusion/exclusion criteria are met. The subjects will be assigned to 1 of 6 groups after the screening period of up to 28 days. Each subject will have 2 marked areas (Area 1 and Area 2) of the abdomen dosed with CCH (single or multiple doses) plus a marked non-dosed control area for comparison. The control area will be located between the 2 treatment areas. Subjects in each group will receive up to 3 CCH doses (each dose as either a [REDACTED] single injection technique or a [REDACTED] e) across 2 treatment areas. Total study duration for each subject is approximately 50 to 71 days depending on the group assigned (not including the screening period of up to 28 days). The duration of the study from first subject first visit to last subject last visit will depend on the ability of the investigative site to identify and enroll eligible 10 subjects.

The study will be conducted in adherence to 3 main activities as follows:

1. Dosing: CCH injections as defined in the protocol
2. Abdominoplasty: Aesthetic elective surgery for the permanent removal/excision of abdominal tissue.
3. Histopathology and Immunohistochemistry of the excised abdominal tissue.

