3.12. Safety Assessments

3.12.1. Adverse Events (AEs)

All AEs occurring after signing the informed consent are to be recorded on the AE pages of the electronic case report form (eCRF). A condition present at baseline that worsens after initiation of study treatment will be captured as an AE; the onset date will be the date the event worsened.

Adverse Events (AEs)

An AE is any unfavorable or unintended change in body structure (signs), body function (symptoms), laboratory result (eg, chemistry, X-ray, etc) or worsening of a preexisting condition associated temporally with the use of the study medication whether or not considered related to the study medication. This would include AEs resulting from concurrent illness, reactions to concurrent medication use, or progression of disease states. AEs include:

- Changes in the general condition of the subject.
- Subjective symptoms offered by or elicited from the subject.
- Objective signs observed by the investigator or other study personnel.
- All concurrent diseases that occur after the start of the study, including any change in severity or frequency of preexisting disease.
- All clinically relevant laboratory abnormalities or physical findings that occur during the study.

Serious Adverse Events (SAEs)

SAEs are those AEs that meet any of the following criteria:

- Results in death
- Life-threatening event

- Results in or prolongs an inpatient hospitalization
- Results in permanent or substantial disability
- Is a congenital anomaly or birth defect
- Any important medical event that may jeopardize the patient or may require medical intervention to prevent one of the outcomes listed above

Adverse Events of Special Interest (AESI)

AEs such as bruising, ecchymosis, hematomas, and contusions that occur remote to the site of drug administration, or any hypersensitivity reactions, including anaphylaxis, will be recorded as an AESI and reported as an AE or SAE as appropriate.

In addition, local AEs associated with the injection site, including bruising, pain, nodules/mass, ulceration, erythema, pruritus, swelling, and/or induration, will be recorded.

Adverse Events Related to Abdominoplasty

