4.4.1.1. Treatment-Emergent Adverse Events (TEAEs)

A TEAE is any condition that was not present prior to treatment with study medication but appeared following treatment, was present at treatment initiation but worsened during treatment, or was present at treatment initiation but resolved and then reappeared while the individual was on treatment (regardless of the intensity of the AE when the treatment was initiated).

The following rules will apply in cases where the start date of an AE is known:

- If the AE onset date is prior to first injection, then the AE will not be considered a TEAE.
- If the AE onset date is equal to or later than first injection, then the AE will be considered a TEAE.

Refer to Section 6.3.1.1 to identify TEAE status when start date of an AE is unknown.

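### SAP 4.4.1.3 imputes a blank causality as related to study drug even for an adverse event that began before the first injection

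*SAP*

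**What the plan says.** SAP 4.4.1.3 groups probably and possibly related as related, and not and unlikely related as negative. It then deals with blanks in one sentence: "Any missing relationship of an AE to study drug will be considered as related to study drug for the analyses, following worst case principle".

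AE recording starts before treatment. SAP 3.12.1 states: "All AEs occurring after signing the informed consent are to be recorded on the AE pages". Protocol 10.3.1 agrees: "AEs will be captured once a subject has signed the informed consent". SAP 3.1 gives the length of the period between: "The subjects will be assigned to 1 of 6 groups after the screening period of up to 28 days".

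The SAP expects AEs in that period, because SAP 4.4.1.1 has a rule for them: "If the AE onset date is prior to first injection, then the AE will not be considered a TEAE". That rule settles treatment-emergent (TEAE) status and does not mention causality.

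For outputs, SAP 7.9.2 plans by-subject AE listings, including one of all AEs. SAP 6.1 has listings show the case report form data together with derived variables. Protocol 9.3.2.1 goes further and has AEs "summarized descriptively by body system, preferred term, severity, and causality", without confining this to TEAEs.

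**The concern.** A worst-case rule should choose the least favourable value that could be true. For an AE that began before the first injection, a causal link to CCH cannot be true, so the rule assigns an impossible value. It also contradicts the TEAE flag that the SAP derives for the same record.

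Safety is a secondary objective, and SAP 6 has the subject narratives draw on the safety listings. A reader of a listing could meet an AE marked related to CCH in a subject who had not yet received CCH, with nothing in the plan requiring a mark to show that the value was imputed.

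**Working it through.** The plan gives no figure to reproduce. The check applies the SAP rules, in order, to each kind of record and looks for any rule that would block the imputation.

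**Inputs.** Start of recording: SAP 3.12.1 and Protocol 10.3.1. TEAE status: SAP 4.4.1.1, or SAP 6.3.1.1 if the start is unknown. Blank causality: SAP 4.4.1.3. Population: SAP 5. Outputs: SAP 6.1 and 7.9.2.

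| Record, in an injected subject | TEAE? | Derived relationship now | With imputation limited to TEAEs |
|---|---|---|---|
| A. Onset after consent, before first injection; blank | No | Related (impossible) | Not related |
| B. As A, but the investigator entered a classification | No | As entered | As entered |
| C. Onset after first injection; blank | Yes | Related | Related |
| D. Onset on the date of first injection; blank | Yes | Related | Related |
| E. Baseline condition that worsens after first injection; blank | Yes, since onset is the date of worsening (SAP 3.12.1) | Related | Related |
| F. Start unknown, ended after first dosing or ongoing; blank | Yes (SAP 6.3.1.1) | Related | Related |
| G. Start unknown, ended before first dosing; blank | No (SAP 6.3.1.1) | Related (impossible) | Not related |

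**Does anything block A or G?** No.

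- SAP 6.3.1.1 uses the first dosing date only to decide TEAE status.
- The Safety Population in SAP 5 selects subjects who were injected. It does not select events by onset, so earlier AEs of those subjects stay in.
- The listing of all AEs in SAP 7.9.2 is not limited to TEAEs.

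**Size.** The documents do not say how many relationship fields will be blank, so no expected count can be given. With no blanks the effect is zero. An upper case for one event: 8 subjects were planned and 2 replacements added, giving 8 + 2 = 10, all assumed injected. If the Protocol 9.3.2.1 summary is produced, and the event falls in a subject with no other related AE, the share of subjects with a related AE rises by 1/10 = 10 percentage points. If the subject already has a related AE, the subject share does not move and only the event count rises by 1.

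**The case against.** The strongest reply is that the case should hardly arise. Protocol 10.3.2 says relatedness must be described on the four-point scale, and Protocol 10.3.4.1 makes the investigator responsible for classifying every AE. *Not related* is available for a screening headache, so a blank is a data-entry gap. This stands, and it is why the point is minor. A reader might infer that blanks will collect in the pre-injection period, but nothing in the documents shows that.

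A reader might also take Protocol 10.3.2 to permit a blank for an AE that starts in screening and continues unchanged, since it says "the relationship would be assessed for the active treatment phase only if the AE worsened". The documents do not support that reading. The sentence belongs to an example about a placebo run-in, which this open-label study does not have. Even there, the AE is assessed for the phase in which it appears. It does not say the field may be left empty.

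It can further be said that the SAP plans AE listings only, tests no hypothesis, and shows the collected data beside derived variables, so a careful reader could compare the onset date with the first injection. That also stands, and it limits the harm. It does not make the derived value correct. Nor does it dispose of the causality summary: SAP 8 says there are no planned changes from the protocol's analysis, so the summary in Protocol 9.3.2.1 has not been withdrawn.

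Finally, limiting imputation to TEAEs leaves an AE that began on the morning of the first injection, before dosing, imputed as related (record D). This is true and acceptable: where only a date separates the two events, the conservative value is at least possible.

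**Conclusion.** The rule is wrong as written, with a small effect. It gives an impossible value for one kind of record: an AE that began before the first injection and has a blank relationship. Pre-injection AEs in general are not turned into drug-related ones, because any AE the investigator classified keeps that classification.

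The consequence is confined to the derived relationship in the AE listings, the narratives that draw on them, and the Protocol 9.3.2.1 summary if it is run. The 10-point figure applies only to that summary, under the assumptions stated with it. A reader might go on to infer a material bias against CCH in the safety results. The documents do not support that: they give no rate of missing causality and require every AE to be classified. The length of screening says how long such AEs can be recorded, not how many will have a blank field.

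**What to change.** Replace the last sentence of SAP 4.4.1.3 with:

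> A missing relationship to study drug will be considered related only for AEs classified as treatment-emergent (Sections 4.4.1.1 and 6.3.1.1); for AEs with onset before the first injection, a missing relationship will be considered not related. Imputed values will be flagged in the listings.

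An AE with unknown start that ended before first dosing (record G) must have begun before it, so the second clause covers it. No safety signal is lost: records C to F are still imputed as related.

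The cost is a short SAP edit, one condition in the AE derivation program and one flag in the AE listing. It needs no new data and no protocol amendment. It should be made before database lock.

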4.4.2. Potentially Clinically Important (PCI) Vital Sign Values

The PCI vital sign values are presented in Table 3 below.

Table 3: Potentially Clinically Important Criteria

Parameter	PCI Low	PCI High
Systolic Blood Pressure	≤ 90 mmHg and decrease ≥ 20 mmHg from baseline	≥ 140 mmHg and increase ≥ 20 mmHg from baseline
Diastolic Blood Pressure	≤ 60 mmHg and decrease ≥ 15 mmHg from baseline	≥ 100 mmHg and increase ≥ 15 mmHg from baseline
Pulse Rate	≤ 50 bpm and decrease ≥ 15 bpm from baseline	≥ 125 bpm and increase ≥ 15 bpm from baseline
Respiratory Rate	≤ 12 brpm and decrease ≥ 7 brpm from baseline	≥ 25 brpm and increase ≥ 7 brpm from baseline
Temperature		$\geq 38.3^{\circ}\text{C}$ and increase $\geq 1.1^{\circ}\text{C}$ from baseline

bpm=Beats per minute; brpm=Breaths per minute

5. ANALYSIS POPULATIONS

The study will use the following analyses population for data summarization:

Table 4: Analysis Population

Population	Definition	Displays
Evaluable Population	The Evaluable Population is defined as all subjects who receive at least 1 injection of study drug and have histopathology and immunohistochemistry results. The histopathology data of the 2 subjects whose abdominoplasty surgery was delayed due to COVID-19, will be analyzed separately.	This population will be used for summarization of demographic and baseline characteristics.
Safety Population	The Safety Population is defined as all subjects who receive at least 1 injection of study drug.	This population will be used for all analyses of subject disposition, demographic and baseline characteristics and safety data listings.

6. STATISTICAL METHODS

There are no statistical hypotheses and analyses planned for the study. Subject narratives will be developed based on the histopathology and immunohistochemistry reports and safety data listings.

6.1. General Methodology

All summary tables and data listings will be prepared using version 9.3 or later of SAS® software (SAS Institute, Cary, NC).

Continuous data will be summarized using descriptive statistics (number of subjects [n], mean, standard deviation [SD], median, minimum [min], and maximum [max]) and discrete data will be summarized using number and percent, the denominator will be based on the number of subjects in the appropriate population. For the purpose of display, the summary results will be rounded as follows:

- Min and max: same number of decimal places as the raw data.
- Mean and median: one more decimal place than the raw data.
- SD: two more decimal places than the raw data.
- Percentages will be displayed with one decimal precision. For zero count, count and percentages will be displayed as “0 (0.0)”.
- The standard form of a percentage change variable is 1 decimal place.

For categorical variables with missing values, a category documenting the frequency of missing values will be displayed in the summary tables.

Summary tables, subject listings and any supportive SAS output will include a “footer” of explanatory notes that will indicate, when applicable:

- Date of data extraction
- Date and time of output generation
- SAS program name, including the path, that generates the output
- Source Dataset

When calculating percentages, the denominator will be based on the number of subjects with non-missing values. If the denominator is expected to change over time, then the denominator used to calculate the percentage should be based on the number of subjects with non-missing values at each visit. Any subject removed from an analysis will be noted at the bottom of the table along with the reason the subject was removed.

Null summary tables will be presented with a note stating that ‘No Subjects Met Criteria.’

Subject listings of all data from the CRFs as well as any derived variables will be presented.

6.2. Derived Variables

Refer to Table 5 below for a list of derived variables and their definitions for study parameters.

Table 5: Derived Variables and Definitions

Variable	Definition
Height (cm)	If height is recorded in inches, then height is equal to the recorded value multiplied by 2.54 and then rounded to 1 decimal point.
Weight (kg)	If weight is recorded in pounds, then weight is equal to the recorded value multiplied by 0.454 and then rounded to 1 decimal point.
Body Mass Index(BMI)	BMI will be computed using height and body weight measured at screening as, $BMI \text{ (kg/m}^2\text{)} = \text{Weight (kg)} / \text{Height (m)}^2$.
Study Day	Study Day will be computed as, Date of Assessment – Date of Day 0 (Surgery Visit).
Baseline	Baseline is defined as the last non-missing measurement/assessment prior to the first dose of study drug.
Change from Baseline	Change from baseline will be derived as, post-baseline visit/time point value – the baseline value.
Last Date in Study	Last date in study is defined as: 
 • The date of Day 28 if the subject completes the study. • The date of early termination if the subject is terminated early from study at a non-scheduled visit. • The date of the latest scheduled visit if the subject is terminated early from study at a scheduled visit or lost to follow-up.
Time in Study	Last date in study - Date of ICF signed in study + 1.
Duration of AE	AE end date – AE start date + 1.
AE Onset Day	AE start date – Date of Day 0 (Surgery Visit) + 1.

ICF=Informed consent

6.3. Handling of Missing Data

Subjects who discontinue from study treatment for any reason after the first dose of study treatment may be replaced at the discretion of the sponsor to ensure the appropriate number of subjects complete the study.

For categorical variables with missing values, a category documenting the frequency of missing values will be displayed in the summary tables.

Immunogenicity samples with a positive titer value will undergo a log transformation for analyses. Samples with titer level less than (<) 10 will be assigned or imputed as a log transformed titer of one (1) for analyses.

